4.1. Protocol Deviations

Important protocol deviations (including deviations related to study inclusion/exclusion criteria, conduct of the trial, subject management or subject assessment) will be summarised and listed.

Protocol deviations will be tracked by the study team throughout the conduct of the study in accordance with the Protocol Deviation Management Plan.

- Data will be reviewed prior to freezing the database to ensure all important deviations are captured and categorised on the protocol deviations dataset.
- This dataset will be the basis for the summaries and listings of protocol deviations.

A separate summary and listing of all inclusion/exclusion criteria deviations will also be provided. This summary will be based on data as recorded on the inclusion/exclusion page of the eCRF.

5. CONSIDERATIONS FOR DATA ANALYSES AND DATA HANDLING CONVENTIONS

Table 1 provides an overview of appendices within the RAP for outlining general considerations for data analyses and data handling conventions.

Table 1 Overview of Appendices

Section	Component
9.1	Appendix 1: Time & Events
9.2	Appendix 2: Treatment States and Phases
9.3	Appendix 3: Data Display Standards & Handling Conventions
9.4	Appendix 4: Derived and Transformed Data
9.5	Appendix 5: Premature Withdrawals & Handling of Missing Data
9.6	Appendix 6: Multicenter Studies
9.7	Appendix 7: Examination of Covariates, Subgroups & Other Strata
9.8	Appendix 8: Multiple Comparisons & Multiplicity
9.9	Appendix 9: Model Checking and Diagnostics for Statistical Analyses.

6. STUDY POPULATION ANALYSES

6.1. Overview of Planned Analyses

The study population analyses will be based on the “Enrolled” OR “FAS” population, unless otherwise specified.

Table 2 provides an overview of the planned study population analyses, with full details of data displays being presented in Appendix 11: List of Data Displays.

Table 2 Overview of Planned Study Population Analyses

Endpoint / Parameter / Display Type	Data Displays Generated		
	Table	Figure	Listing
Subject Disposition			
Subject Disposition	Y		
Reasons for Screen Failure	Y		Y
Reasons for Subject Withdrawal			Y
Subjects by Country and Centre	Y		
Protocol Deviations			
Important Protocol Deviations	Y		Y
Subjects with Inclusion/Exclusion Criteria Deviations			Y [1]
Populations Analysed			
Study Populations and Exclusions	Y		
Subjects Excluded from Any Population			Y
Demographic and Baseline Characteristics			
Demographic Characteristics	Y		Y
Race and Racial Combinations	Y		Y [2]
Medical Conditions and Concomitant Medications			
Medical Conditions			Y
Concomitant Medications	Y		Y

NOTES:

- Y = Yes display generated.

[1] Listing also includes analysis population exclusions.

[2] Listing of race.

7. STATISTICAL ANALYSES

7.1. Exploratory Analyses

7.1.1. Overview of Planned Exploratory Analyses

The efficacy analyses will be based on the “Full Analysis Set” population, unless otherwise specified.

Data Quality Deviators (for data points at each protocol time point):

Activity & Night time Rest endpoints

For all the actigraphy endpoints if the difference between visits of ALSFRS and Actigraphy is more than 21 days then the data will be excluded and will not be used for the summaries. If the first time point within a visit falls within the 21 days window, then all the time points will be considered.

Using the default sleep times for this study (22:00-07:00) which are derived from the day and night anchor times (set by the day/night algorithms used in this study), the amount of data present for a 24-hour recording period was calculated by adding up the durations for activity classifiers: active + sedentary [where sedentary = sedentary not lying + lying]. If the amount of data present is too low (conversely the amount of “off” time is too high) then the data will not be representative of a full day or night, because a subject’s pattern of activity throughout a day or night is not expected to be homogenous or uniform.

A review of the literature showed that a variety of rules can be used, ex. for daytime recordings: 70-75% of data present, 10 of 16 hours (63%) data present. There are not set rules or standards. As this study utilises 22 hours recording (2 hours permitted for charging), the study team decided on the following limits: 70% for the day and 60% for the night. The % is set lower for the night as it was recognised that subjects may have more problems with night (either due to their disease, or with the technology) and so the amount of valid usable data for a night might be expected to be less. [Tudor-Locke, 2012]

Daytime Endpoints

Any data point associated with a 24-hour recording period (1440 minutes), or for a partial recording period, for DAY TIME with <9.1 hours of data for the day time is considered as a data quality data point deviator.

Day = 15 hours, permit 2 hours charging = 13 hours. 70% of 13 hours = 9.1 hours. Exclude data point if active day+sedentary day = <9.1 hours

Night time Endpoints

Any data point for a 24-hour recording period (1440 minutes), or for a partial recording period, for NIGHT TIME with <4.2 hours of data for the night time is considered as a data quality data point deviator.

Sleep = 9 hours, permit 2 hours charging = 7 hours. 60% of 7 hours = 252 mins, 4.2 hours. Exclude data point if active night + sedentary night = <4.2 hours

Night time rest endpoints

Sleep = 9 hours, permit 2 hours charging = 7 hours. 60% of 7 hours = 252 mins, 4.2 hours. Exclude data point if active night + sedentary night = <4.2 hours

Heart Rate Variability (24 hour endpoints only)

The amount of data present over a 24-hour recording period is also important for the 24 hour endpoints for HRV: mean and variance for HRV recorded using RMSSD methods (24 hours). 24-hour RMSSD HRV data with 40% or more data present will be accepted for analysis. The number of time windows that the HRV data is determined from is recorded in the dataset from McLaren. The following data quality rule will be applied:

Number of 5-minute windows (number of data points) in 24 hrs = 288. Allow for 2 hours charging = 24. Leaves 264 data points. Ruling = require 40% or more of data present for the 24-hour time period, otherwise it is not considered as representative of 24 hours. 40% of 264 = 105.6. Therefore, exclude data point if number of 5-minute window (number of data point) < 105.

Speech Endpoints

There is no data quality rule for Speech data as there are no data quality deviators, and all available data will be included in the summary and statistical analysis.

The data quality deviator flags will be populated in the data and the summary tables and figures will be produced for data with the deviator and without the data quality deviator.

[Table 3](#) provides an overview of the planned efficacy analyses, with further details of data displays being presented in [Appendix 11](#): List of Data Displays.

Table 3 Overview of Planned Exploratory Analyses

Endpoint / Parameter/ Display Type	Absolute						Change from Baseline							
	Stats Analysis			Summary		Individual	Stats Analysis			Summary		Individual		
	T	F	L	T	F[1]	F	L	T	F	L	T	F[1]	F	L
Actigraphy - feasibility & Wear time Measures														
Wear Time (active + sedentary time)				Y			Y							
Duration of day time wear time				Y			Y							
Duration of night time wear time				Y			Y							
Actigraphy Diary Data – feasibility measures														
Actigraphy Diary data) (Items 2, 3, 5, 6, 8) And Feasibility				Y			Y							
Device impact Data – feasibility measures														
Device Impact				Y			Y							
Actigraphy - Day/Night measures of physical activity - exploratory efficacy measures 2 measures for 24-hour recording period: Total Activity Score and Maximum Score														
Time Spent Active							Y							
Non-normalised (Average day time active and average night time active) & normalised (% daytime active; % night time active)				Y	Y		Y				Y	Y		
Over All Time Spent sedentary not lying							Y							
Non-normalised (Average day/night time spent sedentary not lying) & normalised (% daytime sedentary not lying; % night time sedentary not lying)				Y	Y		Y				Y	Y		
Over All Time Spent Lying							Y							
Non-normalised (Average day/night over all time spent lying) & normalised (% daytime lying; % night time lying)				Y	Y		Y				Y	Y		
Over All Time Spent Sedentary							Y							

Endpoint / Parameter/ Display Type	Absolute							Change from Baseline						
	Stats Analysis			Summary		Individual		Stats Analysis			Summary		Individual	
	T	F	L	T	F[1]	F	L	T	F	L	T	F[1]	F	L
Non-normalised (Average day/night over all time spent sedentary) & normalised (% daytime sedentary; % night time sedentary)				Y	Y		Y				Y	Y		
Total Activity Score Day/Night (Total Day time Activity score/hour; Total Night Time Activity score/hour)				Y	Y		Y				Y	Y		
Total Activity Score – 24 hour (derived by adding up the day & night scores)				Y	Y		Y				Y	Y		
Maximum Score –24 Hour (Maximum score of day OR night for each 24-hour recording) And Average of 3 values				Y	Y		Y				Y	Y		
Active Periods (Numbers) normalised / hr				Y	Y		Y							
Active Periods (Duration)				Y	Y		Y				Y	Y		
Relationship between the ALSFRS and actigraphy measures	Y	Y						Y	Y					
Actigraphy - Night Time Rest Endpoints - exploratory efficacy measures														
Number Night Time Movement Episodes/Hr (use average)				Y	Y		Y				Y	Y		
Percent Time Night- time Rest Efficiency (use average)				Y	Y		Y				Y	Y		
Rest Fragmentation Index (use average)				Y	Y		Y				Y	Y		
Average Duration Movement Episodes				Y	Y		Y				Y	Y		

Endpoint / Parameter/ Display Type	Absolute						Change from Baseline							
	Stats Analysis			Summary		Individual		Stats Analysis			Summary		Individual	
	T	F	L	T	F[1]	F	L	T	F	L	T	F[1]	F	L
Data Quality Deviators														
Data Quality Deviators for Actigraphy				Y										
Data Quality Deviators for Heart Rate Variability				Y										
Reconciliation for Actigraphy and Diary Data														
Reconciliation of Actigraphy and Diary Data				Y										
Heart Rate Variability Measures (mean & variance) - exploratory efficacy measures														
LF/HF Lying				Y	Y		Y				Y	Y		
LF/HF Active				Y	Y		Y				Y	Y		
LF/HF Sedentary not lying				Y	Y		Y				Y	Y		
LF/HF Active Minus Lying				Y	Y		Y				Y	Y		
LF/HF Sedentary not lying minus Lying				Y	Y		Y				Y	Y		
RMSSD (24 hr average)				Y	Y		Y				Y	Y		
Relationship between the ALSFRS and biotelemetry measures of HRV.	Y	Y						Y	Y					
Quantitative Speech Testing- exploratory efficacy measures														
Change over time in digital speech measures (Group by test) (Test details are in Section 9.4.3)				Y	Y		Y				Y	Y		
Relationship between the ALSFRS and digital measures of speech.	Y	Y						Y	Y					
Relationship between Forced Vital Capacity (FVC) and digital measures of speech.	Y	Y						Y	Y					
ALSFRS-R														
ALSFRS-R Total Score				Y	Y		Y				Y	Y		
FVC														
FVC				Y	Y		Y				Y	Y		

NOTES:

[1] The figures are plotted using the absolute values over time and relative rate of decline of related endpoints. See

Section 7.1.2 for details.

- T = Table, F = Figure, L =Listing, Y = Yes display generated.
- Stats Analysis = Represents TFL related to any formal statistical analyses (i.e. modelling) conducted.
- Summary = Represents TFL related to any summaries (i.e. descriptive statistics) of the observed raw data.
- Individual = Represents FL related to any displays of individual subject observed raw data.

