9.1. Appendix 1: Time & Events

9.1.1. Protocol Defined Time & Events

Table 1 Time and Events – Pilot Phase

Procedures	Clinic Visit	Home Monitoring (~ 3 days)	Telephone Contact ^a (TC)	Repeat Clinic Visit ^b	Home Monitoring ^b (~ 3 days)	Telephone Contact ^{a,b}	EWD
	Screening Day 0						
Informed consent	X						
Eligibility criteria	X						
Demography	X						
Medical and ALS history	X						
Brief neurological exam	X			X			
AEs/SAEs	X		X	X		X	X
Sensor placement	X	X		X	X		
Reference tasks	X			X			
Subject completes diary		X			X		
Site obtains diary information			X			X	X
Device impact questionnaire			X			X	X

- a. Telephone contact to follow the 3-day home monitoring period to ensure the subject has completed the home monitoring period, diary, and to assess AEs, as appropriate. The expectation is that this call would occur on the first weekday following the home monitoring period.
- b. May be repeated as necessary

Table 2 Time and Events – Core Study Phase

Study Day/Week ^a	Screen/Baseline Day 1/Week 0	Weeks 0, 4, 8	Week 12	Weeks 12, 16, 20	Week 24	Weeks 24, 28, 32	Week 36	Weeks 36, 40, 44, 48 ^c	Week 48 or EWD
	Clinic Visit 1 ^b	Home Monitoring (~3 days)	Clinic Visit 2	Home Monitoring (~3 days)	Clinic Visit 3	Home Monitoring (~3 days)	Clinic Visit 4	Home Monitoring (~3 days)	Clinic Visit 5
Procedures									
Informed consent	X ^d								
Eligibility criteria	X ^d								
Demography	X ^d								
Medical and ALS history	X ^d								
Neurological exam	X								
Smoking details	X		X		X		X		X
Brief neurological exam			X		X		X		X
AEs/SAEs ^e	X	X	X	X	X	X	X	X	X
Concomitant medications ^e	X	X	X	X	X	X	X	X	X
ALSFRS-R ^e	X	X	X	X	X	X	X	X	X
FVC	X		X		X		X		X
Speech assessment	X		X		X		X		X
Sensor placement	X	X	X	X	X	X	X	X	X
Reference tasks	X		X		X		X		X
Device impact questionnaire			X		X		X		X
Subject completes diary		X		X		X		X	
Site obtains diary information ^f		X	X	X	X	X	X	X	X
Follow-up Telephone Contact ^g		X		X		X		X	

- a. Clinic visits and home monitoring periods should be conducted within ± 7 days of the scheduled visit/home period and should be scheduled according to the Baseline Visit.
- b. Subjects transitioning from the Pilot Phase do not need to perform these procedures.
- c. The Week 48 home monitoring period will occur the three days prior to the Week 48 in-clinic visit (Visit 5).
- d. Assessed in clinic at Weeks 0, 12, 24, 36, and 48 and by telephone at Weeks 0, 4, 8, 12, 16, 20, 24, 28, 32, 36, 40, and 44.

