- e. Assessed in clinic at Weeks 0, 12, 24, 36, and 48 and by telephone at Weeks 4, 8, 16, 20, 28, 32, 40, and 44.
- f. Diary information should be obtained by telephone at Weeks 0, 4, 8, 12, 16, 20, 24, 28, 32, 36, 40, and 44.
- g. Telephone contact to follow each 3-day home monitoring period. The expectation is that this call would occur on the first weekday following the home monitoring period.

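### The 21-day limit on distance from the ALSFRS-R covers actigraphy but not HRV recorded in the same home monitoring periods

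*SAP*

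**What the plan says.** SAP Section 7.1.1 sets the data quality rules. Under its heading for activity and night-time rest endpoints it states, for every actigraphy endpoint: "if the difference between visits of ALSFRS and Actigraphy is more than 21 days then the data will be excluded". It adds: "If the first time point within a visit falls within the 21 days window, then all the time points will be considered". No reason is given for 21 days.

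The HRV rule in the same section is of another kind. It begins: "The amount of data present over a 24-hour recording period is also important for the 24 hour endpoints for HRV", and it requires at least 40% of the available 5-minute windows. Its heading confines it to the 24-hour endpoints, so it reaches RMSSD only. LF/HF has no quality rule, and no HRV endpoint has a limit on distance in time from the ALSFRS-R.

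Section 7.1.2 correlates HRV with the ALSFRS-R total score, as absolute values and as change from baseline, and restricts the statistical analysis to quality data. Section 2.3 has the accelerometer and the electrode worn together in the home periods.

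On timing, Section 9.1.1, Table 2, footnote a states: "Clinic visits and home monitoring periods should be conducted within ± 7 days of the scheduled visit/home period". The ALSFRS-R is taken in clinic every 12 weeks and otherwise "by telephone at Weeks 4, 8, 16, 20, 28, 32, 40, and 44". The home periods follow the same 4-weekly schedule.

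**The concern.** A proximity limit exists because a sensor value and a functional score taken too far apart do not describe the same disease state. That reason depends on when the home period took place, not on which sensor output is read from it. If the period is too far from the ALSFRS-R for actigraphy, it is equally far for the HRV recorded at the same time. As written, the same period is dropped from one set of correlations and kept in the other.

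The analysis estimates a within-subject correlation over time (Section 7.1.2), which depends on the two series being matched in time. Section 9.7.1 notes that the number of subjects is small, so a few mistimed pairs may carry some weight.

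The width of the limit raises a lesser question. It is longer than half the visit interval, and the SAP gives no explicit rule for which ALSFRS-R a recording belongs to. The closest-assessment wording in Section 9.4.1 chooses among several measurements at one time point. It does not assign recordings to visits.

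**Working it through.** **HRV coverage: the provisions side by side**

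- Actigraphy: 21-day proximity exclusion plus wear-time thresholds (Section 7.1.1).
- RMSSD: completeness count only. The plan's figure reproduces: 288 − 24 = 264 windows, and 0.40 × 264 = 105.6.
- LF/HF: no rule.
- Displays (Section 9.11.4): RMSSD is summarised for all data and for quality data (Tables 2.109–2.115 and 2.120–2.126). LF/HF is summarised for all data only (Tables 2.105–2.108 and 2.116–2.119). A proximity limit on HRV would create a quality-data version of LF/HF, and none is listed.
- Table 2.144 (HRV deviators) asks for a footnote giving three rules, but the text states only one for HRV. The note does not establish a proximity limit.

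The displays therefore agree with the text that HRV has no such limit.

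**Width of the limit: inputs**

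- Interval between visits: 4 weeks × 7 = 28 days (Section 9.1.1).
- Visit window: ±7 days (Section 9.1.1, footnote a).
- Exclusion limit: 21 days (Section 7.1.1).

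**Step 1. Limit against interval.** Half of 28 is 14, and 21 > 14. As a share of the interval, 21/28 = 75%.

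**Step 2. Two scores in reach.** With scores on days 0 and 28, a recording on day t is within 21 days of both when 28 − 21 ≤ t ≤ 21, that is, days 7 to 21. On days 15 to 21 it passes the limit against day 0, although the next score is only 28 − 15 = 13 to 28 − 21 = 7 days away.

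**Step 3. Can Step 2 arise in compliant visits?** With recording and score each within ±7 days of the same nominal date, the largest gap is 7 + 7 = 14 days. So the 21-day rule never excludes a compliant same-visit pair, and days 15 to 21 cannot occur. The next visit's score lies between 28 − 14 = 14 and 28 + 14 = 42 days away. A recording's own score is therefore never strictly farther than its neighbour's; they can only tie, at 14 days.

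**Step 4. If the own-visit score is missing or unevaluable.** Taking every whole day in each window as equally likely gives 15 × 15 = 225 combinations of recording day and next-score day. The gap is 21 days or less in 1 + 2 + … + 8 = 36 of them, and 36/225 = 16%. In those cases a cross-visit pair would pass the limit. Equal weighting is an assumption for illustration.

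**Step 5. A 14-day limit.** It drops no compliant same-visit pair (the maximum gap is 14). It lets a compliant cross-visit pair through in 1 of 225 combinations (0.4%).

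**The case against.** The best defence is that the schedule already ties the score to the recording. Between clinic visits the ALSFRS-R is taken on the telephone call that follows each home period, expected on the first weekday afterwards (Section 9.1.1, footnotes e and g). In clinic weeks the home period follows the visit, and at Week 48 it immediately precedes it. The planned gap is days, for HRV as for actigraphy. The study is also exploratory, has no primary endpoint, and plans no comparison of actigraphy with HRV.

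This stands as a limit on size: the exclusion should seldom act. It does not explain why, when it does act, it should act on one output of a home period and not on the other.

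A reader might go further and infer three things that the SAP does not support.

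- **That the rule pairs recordings with the wrong visit's score.** It says when data are excluded, not how they are paired. Step 3 shows that the 15-to-21-day case needs an assessment out of window. Cross-visit pairing otherwise needs a missing or unevaluable score.
- **That three quarters of a visit-to-visit change becomes timing error.** At an assumed decline of 0.5 to 1.5 points per 30.4 days, 21 days is 0.35 to 1.04 points, against 0.46 to 1.38 over 28 days. That is a worst case. The planned correlations use absolute values and change from baseline over 48 weeks (336 days), of which 21 days is 21/336, or about 6%.
- **That the HRV mismatch is unlimited.** No cap is written, but HRV comes from the same scheduled home periods.

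**Conclusion.** The point stands on HRV. The proximity exclusion is stated for actigraphy only, and the display list agrees. A home period judged mistimed for actigraphy still contributes to the LF/HF and RMSSD correlations. This rests on reading the 21-day exclusion as part of the quality-data definition that governs the correlations. Its place among the data quality deviators in Section 7.1.1 supports that reading, although the sentence itself mentions only summaries.

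The width of the limit is a secondary matter. It bears on out-of-window, missing or unevaluable assessments, and compliant visits with an evaluable own-visit score are unaffected. Whether 21 or 14 days is the better limit is a judgement, and 21 days is not an error in itself.

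The number of recordings affected cannot be derived from the SAP and is probably small. No bias in a correlation coefficient has been demonstrated. The case for acting is that the change alters which pairs are analysed and costs very little.

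**What to change.** - In Section 7.1.1, apply the ALSFRS-R proximity exclusion to all HRV endpoints, LF/HF and RMSSD, and say that it governs the correlation analyses as well as the summaries.
- Add the matching HRV deviator flag and quality-data versions of the LF/HF displays. Make the footnote to Table 2.144 list the HRV rules that actually apply.
- State the pairing rule: each recording goes with the ALSFRS-R of the same nominal visit, and each score is used once. Pairing by nearest date alone could give one score to two recordings, which does not suit a model whose covariance is indexed by visit (Section 7.1.2). Confine the fallback to another assessment in Section 9.4.1 to the same nominal visit.
- Keep 21 days as the main limit, preferably with a reason, and report a 14-day limit as a sensitivity analysis.

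The cost is SAP wording, one derivation and a few added displays. A few HRV recordings would leave the quality-data analysis; they would remain in the all-data displays.

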9.4. Appendix 4: Derived and Transformed Data

9.4.1. General

Multiple Measurements at One Time Point

 For the ALSFRS-R, if the closest assessment is not evaluable, the other assessment would be used.
Study Day

 Calculated as the number of days from baseline visit (visitnum=10 or 90) 
 Ref Date = Missing → Study Day = Missing Ref Date < Baseline Visit Date → Study Day = Ref Date – Baseline Visit Date Ref Date ≥ Baseline Visit Date → Study Day = Ref Date – Baseline Visit Date + 1

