9.11.4. Exploratory Tables

Efficacy: Tables					
No.	Population	IDSL / TST ID / Example Shell	Title	Programming Notes	Deliverable [Priority]
Actigraphy - feasibility & Wear time Measures					
2.1.	FAS	EFF_T1	Summary of Wear Time (mins) (All data)	By visit and Overall Paginate by Pilot Phase and Core Phase	SAC
2.2.	FAS	EFF_T1	Summary of Wear Time (mins) (Quality data)	By visit and Overall Paginate by Pilot Phase and Core Phase	SAC
2.3.	FAS	EFF_T1	Summary of Duration of Day Wear Time (All data)	Same as Above	SAC
2.4.	FAS	EFF_T1	Summary of Duration of Day Wear Time (Quality data)	Same as Above	SAC
2.5.	FAS	EFF_T1	Summary of Duration of Night Time Wear Time (All data)	Same as Above	SAC
2.6.	FAS	EFF_T1	Summary of Duration of Night Time Wear Time (Quality data)	Same as Above	SAC
Actigraphy - Day/Night measures of physical activity - exploratory efficacy measures 2 measures for 24-hour recording period: Total Activity Score and Maximum Score					
2.7.	FAS	EFF_T1	Summary of Time Spent Active (All data)	Categorise into: Average Day/Night Time active %Day Time Active %Night Time Active	SAC

CONFIDENTIAL

201283

Efficacy: Tables					
No.	Population	IDSL / TST ID / Example Shell	Title	Programming Notes	Deliverable [Priority]
2.8.	FAS	EFF_T1	Summary of Time Spent Active (Quality data)	Categorise into: Average Day/Night Time active %Day Time Active %Night Time Active	SAC
2.9.	FAS	EFF_T1	Summary of Change from Baseline of Time Spent Active (All data)	Same as Above	SAC
2.10.	FAS	EFF_T1	Summary of Change from Baseline of Time Spent Active (Quality data)	Same as Above	SAC
2.11.	FAS	EFF_T1	Summary of Relative Rate of Decline of Time Spent Active (All data)	Same as Above	SAC
2.12.	FAS	EFF_T1	Summary of Relative Rate of Decline of Time Spent Active (Quality data)	Same as Above	SAC
2.13.	FAS	EFF_T1	Summary of Monthly Rate of Decline of Time Spent Active (Quality data)	Same as Above	SAC
2.14.	FAS	EFF_T1	Summary of Overall Time Spent Sedentary Not Lying (All data)	Same as Above	SAC
2.15.	FAS	EFF_T1	Summary of Overall Time Spent Sedentary Not Lying (Quality data)	Same as Above	SAC
2.16.	FAS	EFF_T1	Summary of Change from Baseline of Overall Time Spent Sedentary Not Lying (All data)	Same as Above	SAC
2.17.	FAS	EFF_T1	Summary of Change from Baseline of Overall Time Spent Sedentary Not Lying (Quality data)	Same as Above	SAC

CONFIDENTIAL

201283

Efficacy: Tables					
No.	Population	IDSL / TST ID / Example Shell	Title	Programming Notes	Deliverable [Priority]

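### The 21-day ALSFRS-R gap rule is applied to actigraphy summaries that do not use ALSFRS-R, and it conflicts with the SAP's split into all data and quality data

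*SAP*

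**What the plan says.** Section 7.1.1 has a block headed "Data Quality Deviators (for data points at each protocol time point". Its first rule opens with "For all the actigraphy endpoints" and continues "if the difference between visits of ALSFRS and Actigraphy is more than 21 days then the data will be excluded". The consequence is that "the data will be excluded and will not be used for the summaries". No endpoint or table is exempted.

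The day and night wear limits follow in the same block. A recording below either limit "is considered as a data quality data point deviator". The 21-day sentence does not use that phrase.

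The section closes by saying that deviators will be flagged and that "the summary tables and figures will be produced for data with the deviator and without the data quality deviator". Section 9.4.3 (Actigraphy) likewise plans every derivation twice, once on all data and once on quality data, and only the quality version leaves out deviators. Section 9.11.4 carries this into the table titles, starting with "Summary of Wear Time (mins) (All data)" for Table 2.1.

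Section 2.2 lists wear time among the accelerometer measurements. It lists change over time in activity and in night-time rest as endpoints, separately from the relationship between ALSFRS-R and the accelerometer measures.

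**The concern.** Distance to a rating matters when a recording and a rating are analysed as a pair. It does not bear on whether three days of sensor data give a sound wear time or activity level. As written, the rule still removes such recordings from tables in which ALSFRS-R plays no part.

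The feasibility result (wear time) and the change-over-time results could therefore lose usable sensor data because of the timing of a questionnaire. The plan also does not fix which set the affected recordings belong to, so two programmers following it could produce different *All data* tables.

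**Working it through.** **1. What the actigraphy rules measure.** The wear limits reproduce from Section 7.1.1:
- Day: 15 h − 2 h charging = 13 h; 0.70 × 13 = 9.1 h.
- Night: 9 h − 2 h = 7 h; 0.60 × 7 = 4.2 h.

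Both measure how much data the recording contains. The 21-day limit measures the distance between two assessments, and the SAP gives no derivation for it.

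**2. Where a nearby rating is needed** (Section 9.11.4).

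| Actigraphy tables | Content | Uses ALSFRS-R? | Number |
|---|---|---|---|
| 2.1–2.64 | Wear time, activity | No | 64 |
| 2.74–2.101 | Night-time rest | No | 28 |
| 2.65–2.73 | Activity correlations | Yes | 9 |
| 2.102–2.104 | Night-rest correlations | Yes | 3 |

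Unpaired: 64 + 28 = 92. Paired: 9 + 3 = 12. Total: 104.

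Unpaired tables titled *All data*: wear time 3; eight activity endpoints with three each, 24; number of active periods 1; four night-rest endpoints with three each, 12. Sum: 3 + 24 + 1 + 12 = 40.

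The rule's scope does not follow pairing in the other direction either. HRV is correlated with ALSFRS-R (Tables 2.127–2.132) but has no 21-day rule.

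**3. The two readings side by side.**
- *Deviator*, as the heading suggests. The end of Section 7.1.1 and Section 9.4.3 then keep the recording in the 40 *All data* tables. This contradicts the statement that it is not used for the summaries.
- *Prior exclusion*, as the sentence itself says. The recording is then absent from both sets, and the 40 tables are not all data wherever the rule has removed anything.

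The programming note to Table 2.143 asks for three rules to be footnoted but does not name them. The HRV table (2.144) has the same note although Section 7.1.1 gives HRV only one rule, so the note does not settle the matter.

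**4. When the rule can act.**
- *Both assessments done in window.* Section 9.1.1 allows ±7 days for each, so two events for the same week are at most 7 + 7 = 14 days apart, plus any short lag to the telephone call. Exceeding 21 days needs at least one to be off schedule.
- *Rating missing.* The SAP does not say how the gap is then measured. Suppose, as an assumption, it runs to the nearest rating at another visit. Ratings are 4 × 7 = 28 days apart, so on schedule the gap is 28 days, or 23 to 25 days if calls come 3 to 5 days after recording starts. All exceed 21. I then enumerated visit deviations as independent and uniform, with calls 0, 3 or 5 days after recording starts:

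| Visit deviation | Nearest gap (days) | Share of single missed ratings giving more than 21 days |
|---|---|---|
| 0 | 23–28 | 100% |
| up to ±3 days | 17–31 | 69–100% |
| up to ±7 days | 9–35 | 57–68% |

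- *Pilot Phase.* Tables 2.1–2.6 report this phase, but its schedule in Section 9.1.1 has no ALSFRS-R. The gap is undefined there.

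**5. Size.** A count of affected recordings needs the rate of missed or off-schedule ratings and a rule for missing ratings. The SAP gives neither.

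**The case against.** **The rule may be a deviator.** It stands under the deviator heading, and the wear limits beside it also speak of excluding data points that are nevertheless tabulated both ways. A reader might infer that the *All data* tables are certainly not all data, or that recordings are deleted. The SAP does not support that much. The first holds only on the prior-exclusion reading; the second is too strong, since the sentence names summaries and raw-data listings are planned for several endpoints. The contradiction with the words about summaries remains on the deviator reading.

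**The rule may serve visit alignment.** With ±7-day windows, a gap above 21 days usually means that something was well off schedule, and leaving that point out of a by-visit summary is defensible in an exploratory study. But the rule does not test the recording's own date. A recording made on time fails if the rating was late.

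**Wear time may lie outside the rule.** The sub-heading names activity and night-rest endpoints, and Table 3 groups wear time separately. That is arguable, but the rule says all actigraphy endpoints and Section 2.2 counts wear time among them.

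**A missed call need not remove a recording.** A reader might infer that each missed telephone rating does so. With 8 of 13 ratings by telephone and an assumed 5–15% missed, that would be 8/13 × 5% = 3.1% to 8/13 × 15% = 9.2% of recordings. The documents do not support these figures. The missed rate is invented, in-window shifts can bring a neighbouring rating within 21 days, and the rule is silent on missing ratings. The sentence in Section 9.4.1, "if the closest assessment is not evaluable, the other assessment would be used", concerns multiple measurements at one time point and does not authorise borrowing a rating from another visit.

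**Conclusion.** The point stands in two parts. First, the 21-day rule reaches summaries of endpoints that do not use ALSFRS-R: by its wording, all 92 unpaired actigraphy tables, although only the 12 correlation tables need a nearby rating. Second, its status is contradictory: either the sentence conflicts with the reporting of deviators both ways, or up to 40 tables are mislabelled. Both parts rest on the text alone.

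The number of recordings lost is unknown. A reader might also infer that the loss is selective, because subjects who are progressing may miss more ratings. That is possible, but nothing in the SAP shows it.

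This should be corrected before the tables are programmed. It is not critical: the study is exploratory, and the rule has a sensible purpose in the correlation analyses.

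**What to change.** In Section 7.1.1:

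1. Apply the 21-day rule only where actigraphy is paired with ALSFRS-R: Tables 2.65–2.73 and 2.102–2.104, and scatter plots Figures 2.37–2.45 and 2.62–2.64.
2. In the actigraphy summaries (Tables 2.1–2.64 and 2.74–2.101), the time-course figures (2.1–2.36 and 2.46–2.61) and the listings, keep the recording and carry the rule as a flag only. *All data* is then all data, and *Quality data* depends on the wear limits.
3. State that recordings with no ALSFRS-R rating, including those of the Pilot Phase, stay in the unpaired summaries.
4. Name the three rules to be footnoted in Table 2.143.

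The cost is a few sentences and one flag. By-visit numbers may differ slightly between summaries and correlations. Because Section 9.4.3 averages the monthly rate over visits, a slope used in a correlation may also rest on fewer visits than the same slope in its summary table. A footnote can say so.
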